### 13.7.4. Local Tolerability

Local tolerability (incidence of injection site discomfort and erythema/edema) will be summarized by protocol-specified timepoint following SC injections of XP-8121. Specifically, subjective injection site discomfort as reported by the NRS and Discomfort Description and Duration Questionnaire will serve as the data basis. The incidence of any injection site discomfort (score  $>0$  on the ordinal rating scale) will be analyzed descriptively. Descriptive statistics also will be provided for time of onset and duration (of discomfort), and discomfort description (i.e., pain, irritation, itching, etc.).

In addition, erythema and/or edema formation at the injection site will be assessed using the Modified Draize Scale. Counts and percentages of each category on the erythema/edema spectrum will be presented for each scheduled timepoint.

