## 13.5. Study Endpoints

### 13.5.1. Primary Endpoints

- Safety endpoints collectively include incidence, frequency, severity, and relationship to study drug of TEAEs, including clinically significant vital sign measurements, safety laboratory test results, ECGs, and physical examinations
- Tolerability assessments include Modified Draize Scale and Injection Site Discomfort questionnaires
- Geometric mean ratio of the weekly dose of XP-8121 SC (in  $\mu\text{g}$ ) to the daily dose of oral levothyroxine (aka dose conversion factor), where the XP-8121 dose corresponds to the administration immediately preceding collection of blood TSH used to determine normalization at the end of Maintenance Period

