**APPENDIX C. INJECTION SITE DISCOMFORT ASSESSMENT****Numeric Rating Scale for Injection Site Discomfort**

**Investigative Site Instructions:** The subject should complete the 11-point NRS for Injection Site Discomfort at 10 ( $\pm 2$ ) minutes after injection of study drug. The subject will complete the NRS by drawing a circle around the number corresponding to the perceived intensity (severity) of discomfort according to the instructions below. The goal is for the subject to report the amount of discomfort, if any, remaining at each timepoint, as opposed to reporting the transient pain associated with needle insertion.

**Note:** If a subject is unable to physically complete the questionnaire, the subject will indicate the number on the NRS corresponding to their level of discomfort, and study staff will circle it. Documentation will be provided on each completed questionnaire as to who completed the form.

**Subject Instructions:** Ignoring any pain from insertion of the needle, please draw a circle around the number on the scale below that corresponds to the intensity (severity) of any discomfort you are feeling right now at the study drug injection site.

For example, if you are currently feeling no discomfort, you should circle the number “0” on the left end of scale. If you are currently feeling the worst discomfort possible, you should circle number “10” on the right end of the scale.

Source: [Downie et al, 1978](#)

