**Injection Site Discomfort Description and Duration Questionnaire**

**Study Personnel Instructions:** Question 1 should be completed by the subject at 10 ( $\pm 2$ ) minutes after study drug injection. If the answer to Question 1 is ‘Yes’ then complete the following:

- Questions 1a and 1b should be assessed at 10 ( $\pm 2$ ) minutes after study drug injection and,
- Question 1c only should be assessed once discomfort has fully resolved.

If the answer to Question 1 is ‘No’, then questions 1a, 1b, and 1c should not be assessed.

The goal is for the subject to report if they had any discomfort and if there was discomfort, the qualitative nature and duration of discomfort associated with the delivery of study drug, ignoring any transient pain associated with injection of study drug.

**Note:** If a subject is unable to physically complete the questionnaire, the subject will provide verbal responses, which will be recorded on the questionnaire by study staff. Documentation will be provided on each completed questionnaire as to who completed the form.

**Subject Instructions:** Please answer the questions below.

1. Did you have any discomfort from the study drug administration?

Yes  No

If yes,

1a. How would you describe any discomfort you felt from the study drug? (Check **all** that apply):

Pain (e.g., throbbing, soreness, muscle ache)

Itching

Tingling, twitching or numbness

Irritation (e.g., burning, stinging)

Other (specify): \_\_\_\_\_

1b. About how long after the study drug administration did the discomfort start?

(Please enter a number) \_\_\_\_\_ minutes

1c. In total, how long did the discomfort last? (Please enter a number): \_\_\_\_\_ minutes

Source: [Downie et al, 1978](#)

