9.8.7 Local Tolerability

The Modified Draize Scale, Injection Site Discomfort, time until onset (minutes), and duration of discomfort (minutes) will be summarized by descriptive statistics (n, mean, SD, median, minimum, and maximum) by each collection timepoint.

Discomfort description (i.e., pain, irritation, itching, etc.), each severity category for erythema/edema on the Modified Draize Scale, and the category of Injection Site Discomfort Intensity will be summarized by count and percentage by each collection timepoint.

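### The incidence of any injection-site discomfort is counted from a rating of what is felt at 10 minutes, so discomfort already over by then counts as none

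*Protocol*

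**What the plan says.** **Status.** Protocol 13.5.1 places local tolerability among the primary endpoints: "Tolerability assessments include Modified Draize Scale and Injection Site Discomfort questionnaires". SAP 6.6 does the same.

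**Counting rule.** Protocol 13.7.4 names two sources: "subjective injection site discomfort as reported by the NRS and Discomfort Description and Duration Questionnaire will serve as the data basis". It then defines one headline quantity, "The incidence of any injection site discomfort", as a score above 0 "on the ordinal rating scale) will be analyzed descriptively". Onset, duration and description are to be summarized alongside it.

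**Instruments.** Under Protocol 12.8.6 and Table 2 (note q), both are completed once per injection, at 10 (±2) minutes. In Appendix C the NRS asks the subject to mark "the intensity (severity) of any discomfort you are feeling right now at the study drug injection site". Staff are told that the aim is the amount that remains, and a subject with none at that moment circles 0. The Description and Duration Questionnaire opens with Question 1, in the past tense: "Did you have any discomfort from the study drug administration". If the answer is No, "then questions 1a, 1b, and 1c should not be assessed". If it is Yes, type and onset are taken at 10 minutes, and duration once the discomfort has resolved.

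**SAP.** Section 6.9.7 groups the NRS as Mild 1–3, Moderate 4–6 and Severe 7–10, with no group for 0. Section 9.8.7 gives descriptive statistics for the NRS, onset and duration, counts for description, and says that "the category of Injection Site Discomfort Intensity will be summarized by count and percentage by each collection timepoint". Neither section states an any-discomfort count or mentions Question 1. Section 8.1 promises tabulations of all measured data in general terms. Protocol 13 lets the SAP override the protocol only where the two diverge.

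**The concern.** The plan measures whether any discomfort occurred with an item that asks whether discomfort is still present. The two differ for every episode that ends before the rating. The questionnaire given at the same time can record such an episode, but the incidence rule does not use it.

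What is at stake is the accuracy of a descriptive figure inside a primary endpoint. The incidence would be too low. The local-tolerability tables could also appear to disagree, with more subjects having a described or timed discomfort than having any discomfort. A reader would have no label explaining that one table means ever and the other means remaining at 10 minutes.

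**Working it through.** The documents give no expected discomfort rate, duration data or sample-size figure for this measure, so there is no stated figure to reproduce. The check is a reading of the text, followed by an illustration on assumed values.

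**Step 1: which scale the rule refers to.** Protocol 13.7.4 speaks of an ordinal rating scale without naming it. The 11-point NRS is the only scored discomfort instrument in either document; the questionnaire has no score. The rule is therefore NRS > 0.

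**Step 2: how each pattern is counted at one injection timepoint.**

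| Question 1 at 10 min | NRS at 10 min | Meaning | Counted under Protocol 13.7.4 | Counted under Question 1 = Yes or NRS > 0 |
|---|---|---|---|---|
| Yes | > 0 | Discomfort, still present | Yes | Yes |
| Yes | 0 | Discomfort, already over | **No** | Yes |
| No | > 0 | Inconsistent answers | Yes | Yes |
| No | 0 | None so far | No | No |

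The rules differ only in the second row. For example, discomfort from minute 1 to minute 6 gives Question 1 = Yes, a type, an onset of 1 minute, a duration of 6 − 1 = 5 minutes and an NRS of 0. That subject appears in the description, onset and duration tables and counts as none in the incidence. The combined rule can never give a lower count than NRS > 0, so the direction of the difference is fixed.

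**Step 3: whether the SAP replaces the rule.** SAP 6.9.7 and 9.8.7 contain no competing definition of incidence. With no divergence, the protocol's rule stands.

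**Step 4: the time window.** Both instruments are applied at 10 (±2) minutes, and a No to Question 1 closes the remaining items. Reported onset therefore cannot exceed about 10 + 2 = 12 minutes. Duration is not cut off in this way, because item 1c is completed after resolution.

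**Step 5: illustration of size.** Let p be the true share of subjects with discomfort by the 10-minute assessment, and f the share of those who score 0 at that assessment. Both are assumptions.

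Reported incidence = p × (1 − f)

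| p | f = 25% | f = 50% | f = 75% |
|---|---|---|---|
| 10% | 7.5% | 5% | 2.5% |
| 30% | 22.5% | 15% | 7.5% |
| 50% | 37.5% | 25% | 12.5% |

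With all 44 subjects at one timepoint and p = 30%, 44 × 0.30 = 13.2 subjects would have discomfort. The reported numbers would be 13.2 × 0.75 = 9.9, 13.2 × 0.50 = 6.6 and 13.2 × 0.25 = 3.3.

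**The case against.** The strongest reply is that nothing is hidden. Protocol 13.7.4 names both instruments as its data basis, and SAP 9.8.7 summarizes description, onset and duration. Those items are answered only after a Yes, so their counts roughly reveal how many subjects said Yes. SAP 8.1 may also yield a tabulation of Question 1 itself. A reader might infer that the Question 1 answer is collected and never used; these sections do not support that. What stands is narrower: none of these outputs changes the defined incidence, and a Question 1 table could sit beside it with a different number.

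A second reply is that the 10-minute NRS is deliberate, because both instruments aim to exclude transient needle or injection pain. That justifies the NRS as a measure of remaining intensity. It does not make the NRS a measure of any discomfort, since drug-related discomfort can also end before 10 minutes.

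A reader might also infer that discomfort starting after the assessment is lost to the trial. It falls outside these two instruments, and the 30-minute Draize check covers only erythema and edema. It can still surface as an adverse event through spontaneous report, open questioning or observation (Protocol 12.3), with review at every weekly visit (Protocol 11.2 and 11.3). Asking Question 1 again at 30 minutes would be a separate design choice that changes the instrument and the schedule; this point does not require it.

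Finally, the consequence is limited. The trial has a single arm, Protocol 13.7 tests no safety hypotheses, and no alpha, power or decision rule depends on this figure.

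**Conclusion.** The point holds as a defect in the counting rule. As written, the incidence of any injection-site discomfort is the incidence of discomfort still present at 10 (±2) minutes, and it understates the incidence of discomfort felt up to that time. It concerns a descriptive component of a primary endpoint and is worth correcting because the needed answers are already collected.

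The direction is downward; the size is unknown. The illustration rests wholly on assumed p and f and is not an estimate. It would also be wrong to infer that every rating is affected. The maximum of 12 injections (8 in Titration, 4 in Maintenance) × 44 subjects = 528 is a ceiling on ratings taken. Only ratings with Question 1 = Yes and NRS = 0 are misclassified, and the documents do not allow that number to be predicted.

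The conclusion assumes that the rating scale in Protocol 13.7.4 is the NRS, which is the only candidate.

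**What to change.** In Protocol 13.7.4 and SAP 6.9.7 and 9.8.7:

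- Define incidence of any injection-site discomfort as Question 1 = Yes or NRS > 0, reported per injection timepoint and per subject (ever).
- Label the NRS as intensity remaining at 10 minutes, and add None = 0 to the intensity groups.
- State that incidence and onset from these instruments cover only about the first 10 (±2) minutes after injection.

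The cost is a few lines of text and one table row, with no new data collection. The downside is that the reported rate will be somewhat higher and may include some needle pain: the NRS tells the subject to ignore it, whereas for the questionnaire that exclusion appears only in the staff instructions and not in the wording of Question 1. A table footnote should say so.

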### **13.7.5. Physical Examinations**

Findings on the physical examinations will be listed by subject, and abnormal findings will be flagged for clinical significance based on the investigator's judgment.

## **13.8. Other Assessments**

The following assessments will be listed by subject:

- Medical history (coded using MedDRA)
- Pregnancy test
- Urine drug screen

## **13.9. Statistical Issues**

### **13.9.1. Missing or Imputed Data**

No statistical adjustments for missing data will be conducted.

### **13.9.2. Interim Analysis**

No interim analysis will be conducted.

## 14. DIRECT ACCESS TO SOURCE DATA/DOCUMENTS

### 14.1. Study Monitoring

Before an investigational site can enter a patient into the study, a representative of Xeris will visit the investigational study site to:

- Determine the adequacy of the facilities
- Discuss with the Investigator(s) and other personnel their responsibilities with regard to protocol adherence, and the responsibilities of Xeris or its representatives. This will be documented in a Clinical Study Agreement between Xeris and the Investigator.

During the study, a monitor from Xeris or representative will have regular contacts with the investigational site, for the following:

- Provide information and support to the Investigator(s)
- Confirm that facilities remain acceptable
- Confirm that the investigational team is adhering to the protocol, that data are being accurately recorded in the case report forms, and that study drug accountability checks are being performed
- Perform source data verification. This includes a comparison of the data in the case report forms with the patient's medical records at the hospital or practice, and other records relevant to the study. This will require direct access to all original records for each patient (e.g., clinic charts).
- Record and report any protocol deviations not previously sent to Xeris.
- Confirm AEs and SAEs have been properly documented on CRFs and confirm any SAEs have been forwarded to Xeris and those SAEs that met criteria for reporting have been forwarded to the IRB.

The monitor will be available between visits if the Investigator(s) or other staff needs information or advice.

The Medical Monitor will review each proposed subject prior to entering into the Titration Period of the study. The Investigator or designee will complete the Enrollment Authorization Request Form which will detail out the key eligibility criteria and submit to the medical monitor for review and approval.

### 14.2. Audits and Inspections

Authorized representatives of Xeris, a regulatory authority, an IRB or IEC may visit the site to perform audits or inspections, including source data verification. The purpose of a Xeris audit or inspection is to systematically and independently examine all study-related activities and documents to determine whether these activities were conducted, and data were recorded, analyzed, and accurately reported according to the protocol, International Council for Harmonization Good Clinical Practice (GCP) guidelines, and any applicable regulatory requirements. The Investigator should contact Xeris and the IRB/IEC immediately if contacted by a regulatory agency about an inspection.

## **15. QUALITY CONTROL AND QUALITY ASSURANCE**

To ensure compliance with GCP and all applicable regulatory requirements, Xeris may conduct a quality assurance audit. Please see Section [14.2](#) for more details regarding the audit process.

## **16. ETHICS**

### **16.1. Ethics Review**

The final study protocol, including the final version of the ICF, must be approved or given a favorable opinion in writing by an IRB or IEC as appropriate. The Investigator must submit written approval to Xeris before he or she can enroll any patient/subject into the study.

The Investigator is responsible for informing the IRB or IEC of any amendment to the protocol in accordance with local requirements. In addition, the IRB or IEC must approve all advertising used to recruit patients for the study. The protocol must be re-approved by the IRB or IEC upon receipt of amendments and annually, as local regulations require.

The Investigator is also responsible for providing the IRB with reports of any reportable serious adverse drug reactions from any other study conducted with the study drug. Xeris will provide this information to the Investigator.

Progress reports and notifications of serious adverse drug reactions will be provided to the IRB or IEC according to local regulations and guidelines.

### **16.2. Ethical Conduct of the Study**

The study will be performed in accordance with ethical principles that have their origin in the Declaration of Helsinki and are consistent with International Council for Harmonisation of Technical Requirements for Registration of Pharmaceuticals for Human Use (ICH)/GCP, applicable regulatory requirements and the Xeris' policy on Bioethics.

### **16.3. Written Informed Consent**

The Investigator(s) at each center will ensure that the patient is given full and adequate oral and written information about the nature, purpose, possible risk and benefit of the study. Patients must also be notified that they are free to discontinue from the study at any time. The patient should be given the opportunity to ask questions and allowed time to consider the information provided.

The patient's signed and dated informed consent must be obtained before conducting any study procedures.

The Investigator(s) must maintain the original, signed ICF. A copy of the signed ICF must be given to the patient.

## 17. DATA MANAGEMENT

Electronic CRFs (eCRFs) will be employed for this study. Data will be entered into the eCRFs by the study site unless transmitted to Xeris or designee electronically (eg, laboratory data). Queries will be issued for any inconsistencies, omissions, and discrepancies and will be resolved by the appropriate parties. The PI or authorized designee will ensure that all information derived from the source documentation is consistent with the source information and accurately reflected in the CRF. By signing the eCRFs, the PI confirms that the information is complete and correct.

All medical history conditions and AEs will be coded using MedDRA. Concomitant medications will be coded using the current WHO-DD. Data management details will be outlined in a separate data management plan. Following database lock, archive media will be created and forwarded to the clinical site, and the clinical database will be archived.

## **18. DATA HANDLING AND RECORDKEEPING**

### **18.1. Inspection of Records**

Xeris will be allowed to conduct site visits to the investigation facilities for the purpose of monitoring any aspect of the study. The Investigator agrees to allow the monitor to inspect the drug storage area, study drug stocks, drug accountability records, subject charts and study source documents, and other records relative to study conduct.

### **18.2. Retention of Records**

The Investigator must maintain all documentation relating to the study for a period of 2 years after the last marketing application approval, or if not approved 2 years following the discontinuance of the test article for investigation. If it becomes necessary for Xeris or the Regulatory Authority to review any documentation relating to the study, the Investigator must permit access to such records.

## 19. PUBLICATION POLICY

All data generated from this study are the property of Xeris and shall be held in strict confidence along with all information furnished by Xeris. Independent analyses and/or publication of these data by an Investigator or any member of his/her staff is not permitted without prior written consent of Xeris.

Any formal presentation or publication of data from this trial will be considered as a joint publication by the Investigator(s) and appropriate Xeris personnel. Authorships will be determined chiefly by merit, with rights of final authorship decisions to be held by Xeris, unless superseded by an agreement stipulating otherwise. Factors determining merit will include active participation in study design and conduct, as well as interest and ability to participate meaningfully in analyzing or interpreting, writing, or presenting study results. The venue(s) selected for publication will be determined jointly by the publication authors. The first publication will be based on data from all study centers and analyzed as stipulated in the protocol and SAP. Investigators participating in multicenter studies agree not to present data gathered from one study center or a subset of centers before the first full publication, unless formally agreed by Xeris in advance. Written permission to Investigators to publish subset or secondary results will be contingent on prior review by Xeris of the proposed methodology and analytical plan. Any Investigator-led publication or presentation will provide for nondisclosure of Xeris confidential or proprietary information. In all cases, parties planning to publish data agree to submit all draft manuscripts or abstracts to Xeris and other relevant parties at least 60 days prior to publication submission. This will enable involved parties to protect proprietary information and to provide comments to authors.

Further details on the publication process may be provided in individual contractual agreements signed by the Investigators and Xeris.

## **21. APPENDICES**

## APPENDIX A. TITRATION ALGORITHM

- a. Corresponds to 50% of the target weekly dose of XP-8121 (in  $\mu$ g), which is calculated as the current daily oral levothyroxine dose (in  $\mu$ g) multiplied by 4 rounded up to the nearest 50  $\mu$ g.
- b. During the Titration Period, XP-8121 will be titrated based on individual response to therapy (using blood free T4 [fT4] trough concentration as a fast-response, interim biomarker of replacement adequacy) at intervals no more frequent than every other week and in dosage increments corresponding to 25% of the target dose, up to a maximum of 125% of the target dose or 1500  $\mu$ g (whichever is lower).
- c. If a drug-related adverse event is reported or if overdosage is a concern, the Investigator should consult with the Medical Monitor before up-titrating.
- d. Dosing titration decisions should be made after conferring with the Medical Monitor.
- e. Once subjects have completed the Titration Period they will continue at the same dose and time of administration of XP-8121 in the Maintenance Period.

**Note:** Subjects not achieving an adequate fT4 at  $\leq 125\%$  of the target dose or the maximum weekly dose of 1500  $\mu$ g may also continue into the Maintenance Period at the discretion of the Investigator and after conferring with the Medical Monitor.

